2.4 Rationale (CSF – Sub-Study)

HIV replication in the CNS primarily originates from brain macrophages or microglia [40]. Considering those HIV strains that infect macrophages primarily utilize CCR5 (R5 virus) [41], it is not surprising that most HIV strains isolated from individuals with HAD have been R5 tropic [42, 43]. However, paired plasma-CSF samplings from neurologically-asymptomatic HIV-infected individuals across a range of CD4 counts also demonstrate R5 virus, suggesting R5-tropic virus is the predominant stain in the CNS [44]. Potentially, co-receptor utilization may actually mediate neuronal injury. HIV-1 R5 strains isolated from AIDS patients with HAD were highly fusogenic and demonstrated enhanced macrophage tropism despite low of CD4 and CCR5 expression [42, 43]. Although these strains showed reduced sensitivity to anti-CD4-antibodies, the CCR5 inhibitor (TAK-779) appeared to be equally effective as with plasma isolates.

Although markers of immune activation decrease during treated HIV infection, levels can remain abnormally high even after several years of HIV suppression within the plasma and CSF compartments [45, 46]. One explanation is that an inflammatory response, once established, gives rise to a self-sustaining state of macrophage and microglia activation [19]. Activated macrophages produce pro-inflammatory cytokines that both propagate activation-induced apoptosis of uninfected cells and increase blood-brain-barrier (BBB) permeability resulting in enhanced migration of activated T-cells into the CNS. Potentially, the ‘motor’ for neurodegeneration continues after suppression of HIV replication and it is

unknown if MCMD, or other mild HIV cognitive disorders will progress despite potent ARV therapy. In a recent report, the neuropsychological performance of 60% of individuals who had HAND did not normalize despite suppressive HIV therapy [47].

Better penetration of ARVs into the CNS (brain and CSF) is associated with improved neuropsychological performance [8, 9]. Some indirect evidence suggests MVC may achieve therapeutic concentrations in the CNS. In a pilot-study of HIV uninfected women (n=12), MVC 300 mg twice-daily for 7 days achieved exposure levels in cervicovaginal fluid and vaginal tissue comparable or exceeding plasma concentrations [48], suggesting MVC is able to penetrate pharmacokinetic sanctuary sites. In addition, MVC is a substrate for P-glycoprotein (Pgp). Co-administration of ritonavir, a P-gp inhibitor, increased CSF exposure of indinavir by inhibition of P-gp-mediated efflux across the BBB [49, 50]. Potentially, co-administration of a ritonavir-boosted protease-inhibitor (PI/r) will enhance the CNS penetration of MVC.

2.4.1 Hypotheses

1. Maraviroc (MVC) concentrations in CSF will approximate 24% of the plasma C_{min} and will vary across the dosing interval.
 - a. Subjects receiving background HIV therapy containing a PI/r will achieve higher CSF MVC concentrations than those receiving not receiving a PI/r
2. MVC treatment-intensification will decrease immune activation (activated T-cells and pro-inflammatory cytokines) in the CSF.
3. Among subjects with CSF viral replication above 2 copies/mL at baseline, all will be suppressed below 2 copies/mL after 4 weeks of MVC treatment-intensification.

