1.2 Secondary Objectives

- 1.2.1 To compare the rates of phase 2 CD4+ T-cell recovery prior to and during 24 weeks of MVC therapy intensification.
- 1.2.2 To evaluate the impact of MVC therapy intensification on persistent immune activation and maturation phenotype (as measured by flow cytometry) during viral suppression.
- 1.2.3 To characterize differences in the gene expression profiles associated with MVC therapy intensification in individuals receiving a PI/r- vs. NNRTI-based regimen.
- 1.2.4 To evaluate the safety and tolerability of adding MVC to a stable antiretroviral regimen as assessed by the rate of > grade 2 adverse clinical or laboratory events.
- 1.2.5 To characterize cerebral spinal fluid concentrations of MVC compared to plasma concentrations.
- 1.2.6 To evaluate the impact of MVC therapy intensification on persistent immune activation (as measured by soluble and cellular markers) in the central nervous system.

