5.1.1 Dosing

5.1.1.1 with strong CYP3A4 inhibitors, including:

- Protease inhibitors (except tipranavir/ ritonavir)
- Delavirdine
- ketoconazole, itraconazole, clarithromycin, nefazadone, telithromycin
- Darunavir/r + etravirine

MVC 150 mg twice daily

5.1.1.2 with non-inducers/ non-inhibitors of CYP3A4, including:

- Tipranavir/ ritonavir
- Nevirapine
- All NRTIs
- Enfuvirtide

MVC 300 mg twice daily

5.1.1.3 with strong CYP3A4 inducers, including:

- Efavirenz, etravirine
- rifampin

MVC 600 mg twice daily

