9.2.2 Secondary

1. CD4+ T-cell absolute count and percentage at baseline, weeks 4 and 24.
2. The proportion of CD4+/CD8+ T-cell immune activation, maturation, regulatory and apoptosis markers at baseline and weeks 4 and 24.
3. Grades ≥ 2 laboratory abnormalities and signs and symptoms.
4. Paired plasma to CSF ratios of MVC concentration at week 4.
5. Soluble immune activation markers in CSF at baseline and week 4.
6. HIV RNA loads in CSF at baseline and week 4.

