5. Association between change in early immune subsets and phase 2 CD4 recovery will be assessed via Pearson's correlation analysis.

6. MVC plasma to CSF ratios at weeks 4 and 24 will be reported via descriptive statistics. Differences in MVC concentration ratios between subjects receiving a PI/r- vs. NNRTI-based background regimen will be compared via McNemar's test or paired t-tests as appropriate.

7. Descriptive statistics of CNS markers of immune activation will be reported via descriptive statistics. Differences in CNS markers of immune activation between baseline and weeks 4 and 24 will be compared cross-sectionally via McNemar's test or paired t-tests as appropriate.

8. Association between change in CNS markers of immune activation and MVC plasma to CSF ratios will be assessed via Pearson's correlation analysis.

9. Descriptive statistics of toxicity/intolerance during MVC treatment intensification will be reported via descriptive statistics. Differences in proportions of grades > 2 laboratory abnormalities and signs and symptoms will be compared via McNemar's test between time points.

10. Virologic failure during MVC treatment intensification will be reported via descriptive statistics.

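### CSF hypothesis 1a is about maraviroc concentration in CSF, but the only planned regimen comparison of maraviroc exposure uses plasma:CSF ratios, so 1a as written is not tested

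*Combined protocol and SAP*

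**What the plan says.** Section 2.4.1 sets out hypothesis 1, that maraviroc (MVC) "concentrations in CSF will approximate 24% of the plasma" Cmin. Under it, hypothesis 1a says that subjects with a PI/r in the background regimen "will achieve higher CSF MVC concentrations than those receiving not receiving a PI/r".

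The analysis is framed differently:

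- Objective 1.2.5: "To characterize cerebral spinal fluid concentrations of MVC compared to plasma concentrations". Regimen is not mentioned.
- Endpoint 4 in section 9.2.2: "Paired plasma to CSF ratios of MVC concentration at week 4". CSF concentration on its own is not a listed endpoint.
- Section 9.4.3.1, item 6: "MVC plasma to CSF ratios at weeks 4 and 24 will be reported via descriptive statistics", and then "Differences in MVC concentration ratios between subjects receiving a PI/r- vs. NNRTI-based background regimen will be compared", by McNemar's test or paired t-tests.

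Section 3.2 names MVC concentration as a primary outcome of the sub-study, and section 3.6 has MVC assayed in both plasma and CSF, so the data needed for 1a will exist. Section 3.2 also refers once to population pharmacokinetic modelling, without a model, a regimen covariate or a test.

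Under section 5.1.1 the dose depends on the background regimen: "MVC 150 mg twice daily" with most protease inhibitors, 300 mg twice daily with nevirapine, and "MVC 600 mg twice daily" with efavirenz or etravirine.

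**The concern.** The hypothesis and the analysis have different targets. A CSF concentration shows what level subjects reach in the CNS on the dose they were given. A plasma:CSF ratio shows how much of the drug in plasma crosses into CSF. If plasma exposure differs between the regimen groups, one can change without the other. The sub-study could then report no regimen difference in item 6 while 1a was true, or a difference in item 6 that did not bear on 1a.

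The plan does not say which measure decides 1a. If that stays open until the assay results are in, either measure could be presented as the answer. The plan also gives no expected direction for the ratio. Because plasma is the numerator, better penetration shows as a lower value, which is easy to misread.

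**Working it through.** **1. Is CSF concentration compared by regimen anywhere in section 9.4.3.1?**

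| Items | Subject | CSF MVC concentration by regimen? |
|---|---|---|
| 1, 4, 5 | CD4 recovery, T-cell markers | No |
| 2, 3 | CD4 recovery and gene expression by regimen | No (other outcomes) |
| 6 | Plasma:CSF ratio, described and compared by regimen | No (ratio only) |
| 7 | CNS activation markers | No |
| 8 | CNS marker change against the ratio | No |
| 9, 10 | Toxicity, virologic failure | No |

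Item 6 is therefore the only regimen comparison of MVC exposure. The group definitions are not the problem: criterion 4.1.4 requires a PI/r or an NNRTI, so at entry the subjects without a PI/r are in effect those on an NNRTI.

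**2. When do the two measures agree?**

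For PI/r against NNRTI, on the log scale:

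difference in log(plasma:CSF) = difference in log(plasma) − difference in log(CSF).

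If plasma does not differ, the ratio moves by exactly the inverse of CSF. Otherwise it does not. The reference ratio below is 1/0.24 = 4.17, from the 24% in hypothesis 1. That figure refers to Cmin, so it serves only as a scale. All fold changes are assumptions.

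| PI/r plasma | PI/r CSF | Plasma:CSF | 1a | Ratio against reference |
|---|---|---|---|---|
| ×1 | ×1.5 | 4.17 × 1/1.5 = 2.78 | true | lower |
| ×2 | ×2 | 4.17 × 2/2 = 4.17 | true | same |
| ×2 | ×1.5 | 4.17 × 2/1.5 = 5.56 | true | higher |
| ×0.6 | ×0.9 | 4.17 × 0.6/0.9 = 2.78 | false | lower |

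The first and last rows give the same ratio with opposite answers on 1a, so the ratio alone cannot settle it.

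**3. How much data is there?**

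The one planning figure for the sub-study reproduces: 17 subjects × 2.5 lumbar punctures = 42.5, stated as about 43. That total includes pre-treatment punctures. If every subject has one of these, 17 × 1.5 = 25.5 are on MVC, and at most 17 fall at week 4.

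**4. What would a direct comparison deliver?**

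The inputs are 17 subjects from the documents and, as assumptions, an 8/9 split, two-sided alpha 0.05 and the CVs shown. The log SD is s = √ln(1 + CV²), the standard error is s × √(1/8 + 1/9) = 0.486s, and t with 15 df is 2.131. Power is from the noncentral t. The CI factor is exp(2.131 × 0.486s), by which the estimate is divided and multiplied to give the 95% limits.

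| CV | s | Power, CSF ratio 1.5 | Ratio 2 | Ratio 3 | CI factor |
|---|---|---|---|---|---|
| 40% | 0.385 | 53% | 93% | >99% | 1.49 |
| 60% | 0.555 | 29% | 67% | 97% | 1.78 |
| 100% | 0.833 | 16% | 36% | 72% | 2.37 |

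With a 5/12 split at CV 60%, power is 25%, 59% and 94%. These figures are for an unadjusted comparison. Adjusting for sampling time costs about one degree of freedom and may reduce the residual variance. The documents give no CV, effect size or split, so this is a range and not a forecast.

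**The case against.** The strongest reply is that the ratio is right and only the wording of 1a is loose. Hypothesis 1a sits under a hypothesis scaled to plasma, its rationale in section 2.4 is that ritonavir may improve penetration by inhibiting P-gp, and objective 1.2.5 and the listed endpoint both set CSF against plasma. This stands as a reason to keep the ratio and as an alternative way to resolve the mismatch. It does not make 1a tested as written. The paired ratio is also not scaled to Cmin, since punctures are deliberately spread from 2 to 12 hours after dosing.

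A reader might infer from the different doses that item 6 will point the opposite way to 1a. The documents do not support that. Section 2.2.1.2 says dose adjustment is required because CYP3A and P-gp inhibitors and inducers change MVC pharmacokinetics, so a difference in nominal dose does not establish a difference in plasma exposure. Adjustment may shrink or remove such a difference. A reversal is possible only under assumed plasma differences like those in the table.

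It can also be said that population pharmacokinetic modelling might cover 1a. With no regimen term or test specified, it cannot be counted as a planned analysis of it.

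Finally, this is a sub-hypothesis in a small sub-study of a pilot, and no sample size or decision rule rests on it. That limits the consequences but does not remove the mismatch.

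**Conclusion.** Hypothesis 1a as written has no planned test. That follows from the text alone and needs no numerical assumption. Whether the ratio would give a different answer from the concentration is conditional on plasma exposure differing by regimen, and the documents supply no levels from which to judge it. The supportable statement is that the two measures need not agree, not that they will conflict.

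The point is worth settling before the assay results are examined. Its reach is confined to the sub-study's regimen question. No planning figure in the protocol is wrong because of it. Under the assumed 8/9 split, power for a two-fold CSF difference runs from 93% (CV 40%) to 36% (CV 100%), so the confidence interval will be more informative than the p-value, and a null result would say little about modest differences.

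**What to change.** In section 9.4.3.1, item 6:

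1. Add an unpaired comparison of log CSF MVC concentration at week 4 between PI/r and NNRTI subjects, as dosed, adjusted for post-dose sampling time (the 2–6 h and 6–12 h intervals of section 3.2, or time as a continuous covariate). Report the geometric mean ratio with its 95% CI and state that 1a is judged on it. The adjustment matters because hypothesis 1 itself expects CSF levels to change between doses, and chance imbalance in timing is likely in groups this small.
2. Keep the ratio comparison as the separate measure of penetration, and state that a lower plasma:CSF ratio means better penetration. It too needs an unpaired method, because the regimen groups are independent.
3. Add CSF MVC concentration at week 4 to the endpoints in section 9.2.2.

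If penetration was always the intended hypothesis, reword 1a in terms of the ratio, with its direction. Steps 1 and 3 are then unnecessary.

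The cost is SAP wording and, on the first route, one more unadjusted secondary comparison with limited precision. No new samples or assays are needed.

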[contact]
[contact]

SCHEMA

The Impact of CCR5 Inhibitor Treatment Intensification on CD4+ T-cell Recovery and Gene Expression Profiles in HIV-Infected Patients with Viral Suppression (Main Study)

Maraviroc Pharmacokinetics and Immunomodulatory Effects within the Central Nervous System (CSF Sub-Study)

Design:

CCTG 590 is a single-arm, open-label study to evaluate the impact of therapy intensification of Maraviroc (MVC) (a CCR5 inhibitor) to a stable suppressive HIV antiretroviral regimen on the rate of CD4+ T-cell recovery and gene expression profiles. Subjects on a stable first-line HIV regimen with continued viral suppression and sub-optimal CD4+ T-cell counts will be eligible for this study. Those who are found to be eligible will have MVC (dose-adjusted to background HIV regimen) added to their current HIV regimen for 24 weeks. After the 24 week intensification, the MVC will be discontinued, the original antiretroviral regimen will be continued and the subjects will be followed for an additional 12 weeks.

CCTG 590s is a central nervous system (CNS) sub-study that will evaluate MVC cerebral spinal fluid (CSF) pharmacokinetics and immunomodulatory effects within the CNS. The primary eligibility criteria will be enrollment into the MVC parent study, ability to give informed consent to lumbar puncture (LPs). Pre-treatment LPs will be performed, followed by a LP at week 4 of MVC treatment intensification (i.e., “steady state”). For subjects willing to undergo more than one LP, an additional LP will be performed at week 24 of MVC treatment intensification.

Duration:

Total study duration is 36 weeks: 24 weeks of MVC treatment intensification, followed by an additional 12 weeks of continued monitoring on baseline antiviral therapy without MVC.

Sample Size: 30 subjects (17 subjects for the CSF Sub-Study)

Study Population:

HIV-infected patients receiving an initial stable antiretroviral regimen with 12 months or more of viral suppression (defined by HIV RNA below detection limits) will be offered enrollment into this study. Eligible patients must have

documented dates of initiation of first HIV regimen and have been on continuous treatment for at least 15 months. In addition, available laboratory data must include at least 3 measurements of CD4 count and plasma HIV RNA loads obtained within the 12 months prior to screening.

Regimen:

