3.2 Study Design (CSF Sub-Study)

This is a sub-study of the MVC treatment-intensification protocol (i.e., a “piggyback” protocol). The primary eligibility criteria will be enrollment into the MVC parent study, ability to give informed consent to lumbar puncture (LPs), and the absence of medications or conditions that would contraindicate lumbar puncture (e.g., coagulopathy). Pre-treatment LPs will be performed, followed by a LP at week 4 of MVC treatment intensification (i.e., “steady state”). All LPs will be performed within one hour of a parent protocol-dictated blood draw, reducing the need for separate visits or additional phlebotomy. For subjects willing to undergo more than one LP, an additional LP will be performed at week 24 of MVC treatment intensification. The primary study outcomes will be measurement of MVC concentrations and reductions in markers of immune activation levels in CSF at week 4.

The study will aim to obtain 3 LPs in as many subjects as possible with the goal being at least two LPs separated by at least 4 weeks in up to 17 participants. After informed consent is obtained, subjects will undergo a brief screening to ensure the absence of contraindications to LP. If eligible subjects choose to enroll, subsequent visits will occur at major visits of the parent protocol (baseline, week 4 and 24). Based on prior experience we conservatively estimate that approximately 60% of subjects in the parent protocol will be willing to consent to lumbar puncture an average of 2.5 LPs per consenting subject. In total, we estimate that this CSF sub-study will yield approximately 43 LPs from individuals taking MVC. Post-dose timing of the lumbar punctures will be limited by the parent protocols but we will strive to vary the post-dose lumbar puncture interval in order to have approximately equal representation from two intervals.

- Interval 1: 2 - 6 hours post dose
- Interval 2: 6 - 12 hours post dose

If successful, this variation across the dosing interval will improve the accuracy of population pharmacokinetic modeling.

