3.6 Lumbar Puncture

Standard lumbar puncture-related adverse events will be monitored following all visits. Lumbar punctures will be performed under aseptic conditions at the clinical facilities of the HNRC by a neurologist, an internist, or by a trained registered nurse working under the supervision of the neurologist. Standard risks associated with HNRC medical procedures include 1) venipuncture: the risk of pain, bruising, and a very low risk infection; and 2) lumbar puncture: the risk of pain, bruising and a very low risk of infection as well as a risk of post-dural puncture cephalgia which can range from mild to severe.

Routine clinical lab assays (cell counts, glucose, total protein) will be performed on all CSF. HIV RNA will be measured with a modified version of the Biomerieux assay validated to quantify HIV as low as 2 copies/mL in CSF [51]. MVC concentrations will be measured in plasma and CSF. Remaining specimens will be aliquoted and then stored at -70C at the HIV Neurobehavioral Research Center (HNRC) Specimen Bank.

Local back pain will be minimized by injection of an anesthetic, 1% lidocaine into the subcutaneous tissue surrounding the needle puncture site. Oral analgesics and anti-inflammatory medications will be provided when necessary. Following LP, patients will be observed for 10-15 minutes. Over 3,000 LPs have been performed at the HNRC using non-cutting or "pencil point" spinal needles that reduce the risk of post-LP cephalgia. A site clinician will be available by pager 24 hours-per-day to respond to problems, should they occur. If post-LP headache occurs, initial conservative management will include recumbency, hydration, and oral analgesics. When headaches are prolonged, a blood patch, involving an epidural injection of a sample of the subject's own blood, may be performed by consulting anesthesiologists. This is extremely effective in aborting post-LP headache, but is only necessary in fewer than 1% of HNRC subjects. Palliative procedures will be performed at no cost to the participant.

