6.3.13 Lumbar Puncture

For subjects enrolled in the CSF Sub-Study: CSF will be collected at baseline, weeks 4 and 24 for cell counts, protein, glucose, HIV RNA and markers of immune activation.

Cerebral Spinal Fluid volume: 25 mL

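### The CSF virology hypothesis looks only at subjects above the assay limit at one baseline LP, and no numbered analysis item names the CSF HIV RNA endpoint

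*Combined protocol and SAP*

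**What the plan says.** - **Hypothesis.** Section 2.4.1, item 3, reads: "Among subjects with CSF viral replication above 2 copies/mL at baseline, all will be suppressed below 2 copies/mL after 4 weeks" of MVC intensification.
- **Assay.** Section 3.6 describes the CSF HIV RNA assay as "validated to quantify HIV as low as 2 copies/mL in CSF", so the cut-off and the quantification limit are the same value.
- **Sampling.** Section 6.3.13 says "CSF will be collected at baseline, weeks 4 and 24 for cell counts, protein, glucose, HIV RNA and markers of immune activation". The laboratory schedule in section 6.1 shows one LP before MVC, at Day 0, and none at screening or pre-entry.
- **Design and size.** The Schema says "CCTG 590 is a single-arm, open-label study" and gives the sample size as "30 subjects (17 subjects for the CSF Sub-Study").
- **Endpoint.** Section 9.2.2, item 6, is "HIV RNA loads in CSF at baseline and week 4". It carries no subset and no cut-off.
- **Analysis.** In section 9.4.3.1, items 6 to 8 cover MVC concentration ratios and CNS immune-activation markers. Item 10 is "Virologic failure during MVC treatment intensification will be reported via descriptive statistics", and section 6.2.7 defines such failure by plasma HIV-1 RNA. The section's opening sentence promises descriptive summaries and pre/post significance tests for the secondary analyses in general. It gives no method, population or handling of low values for CSF HIV RNA.
- **Objectives.** Neither CNS objective (1.2.5, 1.2.6) mentions CSF HIV RNA.

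**The concern.** Hypothesis 3 is the only specific statement of how the CSF HIV RNA endpoint would be judged. It selects subjects because one reading was above a cut-off, then asks whether the next reading is below it. With visit-to-visit and assay variation, some of those subjects will fall back with no drug effect, and a single-arm design cannot separate that from an MVC effect. The mirror-image movement, from at or below 2 copies/mL at baseline to above it on MVC, is not part of the hypothesis. Eligible subjects are plasma-suppressed, so CSF values close to the limit are plausible. That is an inference; the documents give no CSF HIV RNA distribution.

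At stake is a summary such as the proportion of baseline-positive subjects suppressed at week 4, which would look favourable even if nothing had changed. The word *all* creates a second problem in the opposite direction: a single noisy value above 2 copies/mL refutes the hypothesis despite a real effect. A reading of exactly 2 copies/mL falls in neither category.

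**Working it through.** **1. The plan's own figures.** Section 3.2 expects that "approximately 60% of subjects in the parent protocol will be willing to consent to lumbar puncture", with 2.5 LPs per consenting subject. 0.60 × 30 = 18, against the stated 17. 17 × 2.5 = 42.5, which rounds to the stated 43 LPs. These agree to within rounding. The plan states no power or effect size for CSF HIV RNA.

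**2. Model with no drug effect.** Each subject has a stable log10 CSF level (between-subject SD *sb*), and each visit adds independent error (SD *sw*, biological plus assay). The distribution is the same at both visits. From the documents: the cut-off of 2 copies/mL and n = 17. Assumed: *sb* 0.5 to 1.0, *sw* 0.3 to 0.5, population mean *d* = 0 to 1 log10 below the cut-off.

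- Correlation between visits: r = sb² / (sb² + sw²).
- Share above the cut-off: p = 1 − Φ(d / √(sb² + sw²)).
- Chance that a baseline-positive subject reads below at week 4: q = [Φ(z) − Φ₂(z, z; r)] / p, with z = d / √(sb² + sw²).
- Chance that all baseline positives fall, given at least one: [(1 − p + pq)^17 − (1 − p)^17] / [1 − (1 − p)^17].

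| d | sb | sw | r | p | expected positives of 17 | q | all fall |
|---|---|---|---|---|---|---|---|
| 0 | 1.0 | 0.3 | 0.92 | 0.50 | 8.5 | 0.13 | 0.0001 |
| 0 | 0.5 | 0.5 | 0.50 | 0.50 | 8.5 | 0.33 | 0.001 |
| 0.5 | 1.0 | 0.3 | 0.92 | 0.32 | 5.4 | 0.18 | 0.005 |
| 0.5 | 0.5 | 0.3 | 0.74 | 0.20 | 3.3 | 0.41 | 0.10 |
| 0.5 | 0.5 | 0.5 | 0.50 | 0.24 | 4.1 | 0.53 | 0.12 |
| 1.0 | 0.5 | 0.5 | 0.50 | 0.08 | 1.3 | 0.71 | 0.56 |

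Fifth row worked through: (0.760 + 0.240 × 0.528)^17 = 0.887^17 ≈ 0.130; 0.760^17 ≈ 0.009; (0.130 − 0.009) / (1 − 0.009) ≈ 0.12.

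Over the declared ranges, q runs from 0.13 to 0.71. The top value belongs to a scenario with about one positive subject. Where about 20% to 33% are positive (d = 0.5), q is 0.18 to 0.53 and the chance that all fall is 0.5% to 12%.

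**3. Rises balance falls.** In the fifth row, expected falls are 17 × 0.240 × 0.528 ≈ 2.15, and expected rises are 17 × 0.760 × 0.166 ≈ 2.14, equal apart from rounding. Hypothesis 3 covers the falls only.

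**4. Second parameterisation.** Assume directly that 20%, 30% or 50% are positive, with visit correlation 0.3 to 0.9. Then q is 14% to 67%. The chance that all fall is 4% to 30% at 20% positive, 1% to 10% at 30%, and at most 0.2% at 50%.

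**5. Counting noise alone.** If the reading were a Poisson count with constant mean 2 (assumption), P(>2) = 1 − 5e⁻² = 0.32 and P(<2) = 3e⁻² = 0.41.

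**6. What 17 subjects can show.** The exact 95% lower bound for k of k suppressed is 0.025^(1/k): 29% for 3 of 3 and 48% for 5 of 5. Two-sided exact McNemar gives 2 × 0.5⁵ = 0.063 for 5 falls and 0 rises, and 2 × 0.5⁶ = 0.031 for 6 and 0. With 3 to 5 positives (20% to 30% of 17), even complete suppression cannot reach p < 0.05.

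**The case against.** A hypothesis is a prediction, not an analysis rule. Endpoint 6 has no subset, CSF HIV RNA is to be measured in every sub-study subject, and no passage excludes subjects at or below 2 copies/mL. A reader might infer that the plan will ignore rises or cannot reveal a worsening. The documents do not say so; rises are simply outside the hypothesis, and the data to count them will exist.

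A reader might also infer that the endpoint has no analysis at all. That is too strong, because the opening sentence of section 9.4.3.1 reaches it generically. The gap is one of specification.

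A third tempting reading is that noise would readily confirm hypothesis 3. The 13% to 71% is a per-subject figure and does not measure the stated criterion, which requires *all* to fall. That criterion is rarely met by chance unless very few subjects are positive. Every variability input is also assumed.

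Finally, this is a pilot study, section 3.2 names MVC concentrations and immune-activation markers as the sub-study's primary outcomes, and no decision rests on this endpoint.

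All of this stands, and it limits the size of the point. What remains is that the one specific statement about the endpoint selects on an unconfirmed reading at the assay limit, without a control, and no named analysis corrects for it.

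**Conclusion.** The point holds as a minor one. Section 9.4.3.1 should name an analysis for secondary endpoint 6, and hypothesis 3 is a poor basis for it. A proportion suppressed among baseline positives would be inflated by spontaneous falls, about 13% to 71% per subject with no drug effect. The literal *all* criterion is met by chance far less often: about 0.5% to 12% with roughly 20% to 33% of 17 subjects positive, and up to about 56% with only about one positive. It is also fragile, since one noisy reading defeats it. With 3 to 5 positives, neither outcome would say much about MVC.

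These sizes rest on assumed between- and within-subject SDs, an assumed mean level relative to the cut-off, and a normal model on the log10 scale. The structural facts come from the documents: the cut-off at the assay limit, one pre-MVC LP, a single arm, and no numbered item for the endpoint. The documents do not support saying that the plan will falsely credit MVC with clearing CSF virus.

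**What to change.** Add an item to section 9.4.3.1 for endpoint 6, covering all sub-study subjects with paired LPs:

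- a shift table of CSF HIV RNA above versus at or below 2 copies/mL, baseline against week 4, and against week 24 where that LP was done;
- crossings in both directions, with exact confidence intervals;
- values below the limit treated as left-censored in any summary of paired change, noting that few values may be quantifiable;
- an exact McNemar test as supportive at most, stating that it needs at least 6 falls and 0 rises for p < 0.05.

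Restate hypothesis 3 as a net reduction in the proportion above 2 copies/mL among all sub-study subjects, which also assigns a reading of exactly 2. Describe the result as descriptive and uncontrolled: the two-way count removes the selection artefact but does not supply a control group.

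The cost is wording only. The planned LPs and assays already provide the data. The downside is a more modest claim on an exploratory secondary endpoint.
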